6.4 CONCOMITANT THERAPY

The following concomitant medications are prohibited during the study:

1. Oral corticosteroids
2. Proton Pump Inhibitors (PPIs)

7 STUDY INTERVENTION DISCONTINUATION AND PARTICIPANT DISCONTINUATION/WITHDRAWAL

7.1 DISCONTINUATION OF STUDY INTERVENTION

Withdrawal criteria

Participants **must** be withdrawn from the study if any of the following events occur:

1. Participant experiences intolerable AEs, including clinically relevant abnormal laboratory findings that, in the opinion of the investigator, preclude further participation in the study.
2. Participants who are unable to tolerate study diet and/or for whom the provider discontinues study diet will be withdrawn from the study.
3. Participants unable or unwilling to adhere to dietary restrictions will be withdrawn from the study.
4. Investigator's decision that withdrawal from further participation would be in the participant's best interest.

Participants **may** be withdrawn from the study if any of the following events occur:

1. Participant has any clinically relevant change in medical or psychiatric condition and in the opinion of the investigator, the condition warrants discontinuation from the study.
2. Participant requires a medication that is not permitted by the protocol.

Investigators should attempt to obtain information for participants who withdraw or discontinue. For participants considered as lost to follow up, the investigator should make an effort (at least 1 phone call and 1 written message to the parent[s] or legal representative[s]/caregiver[s]), and document his/her effort (date and summary of the phone call and copy of the written message in the source documents), to complete the final evaluation. All results of these evaluations and observations, together with a narrative description of the reason(s) for removing the participant, must be recorded in the source documents. The Case Report form (CRF) must document the primary reason for withdrawal or discontinuation.

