1 PROTOCOL SUMMARY

1.1 SYNOPSIS

Title:	Food Additive Removal Diet for Pediatric Eosinophilic Esophagitis (FREE)
Study Description:	Prospective, pragmatic standard of care clinical trial comparing dietary therapies of dairy elimination diet (DED) to dairy + food additive elimination diet (FREE) in children with eosinophilic esophagitis.
Objectives:	
Primary Objective: To compare histologic outcomes (eosinophils per high power field: eos/hpf) of dairy elimination diet (DED) to dairy + food additive elimination diet (FREE) in children with eosinophilic esophagitis.
 
Secondary Objective: To compare endoscopic outcomes (Eosinophilic Esophagitis Endoscopic Reference scores: EREFs) of dairy elimination diet (DED) to dairy + food additive elimination diet (FREE) in children with eosinophilic esophagitis
 
Tertiary Objectives: To compare symptomatic (Pediatric Eosinophilic Esophagitis Symptom Severity Module v2.0: PEES) and quality of life (Peds-QL EoE Module 1) outcomes of dairy elimination diet (DED) to dairy + food additive elimination diet (FREE) in children with eosinophilic esophagitis

Endpoints:	
Primary Endpoint: (1) Histologic change differences of maximum eos/hpf baseline vs 12 week endoscopy
 
Secondary Endpoint: (1) EREFs: Eosinophilic Esophagitis Endoscopic Reference Score baseline vs 12 weeks
 
Tertiary Endpoints: (1) Patient Reported Outcomes (Pediatric Eosinophilic Esophagitis Symptom Severity Module (PEES) baseline vs 12 weeks, (2) quality of life (PedsQL-EoE)¹ baseline vs 12 weeks

Study Population:	We will plan to enroll 72 patients. Based on histologic primary outcome efficacy estimates of DED (50%) compared to FREE (estimated 70%) and a sample size of 36 enrolled patients per group (72 total) with 88% power, we will be able to demonstrate a detectable difference of 30% among two

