6.3 STUDY INTERVENTION COMPLIANCE

Study Coordinators will call participants/parents at weeks 2, 3, 5, 6, 8, and 10 to assess difficulty adhering to dietary protocols. If a participant is found to be persistently noncompliant with the diet, the investigator will make a decision as to whether the participant should be withdrawn from the study.

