7.3 LOST TO FOLLOW-UP

Participants will be withdrawn from the study / considered LTFUP if the coordinator is unable to make contact by telephone to complete weekly assessments for at least 3 sequential weeks.

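### Section 7.1 takes those who cannot follow the diet out of the study, and no rule covers a missing week-12 count, so the intention-to-treat comparison defaults to participants with a week-12 count

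*Combined protocol and SAP*

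**What the plan says.** - **Withdrawal.** Section 7.1 lists events after which withdrawal is mandatory. Two concern the diet: "Participants who are unable to tolerate study diet and/or for whom the provider discontinues study diet will be withdrawn from the study" and "Participants unable or unwilling to adhere to dietary restrictions will be withdrawn from the study". Section 7.3 adds a third route, three consecutive weeks without contact: "Participants will be withdrawn from the study / considered LTFUP if the coordinator is unable to make contact by telephone". For persistent noncompliance, 6.3 says that "the investigator will make a decision as to whether the participant should be withdrawn from the study".
- **Follow-up after withdrawal.** Section 7.1 says "Investigators should attempt to obtain information for participants who withdraw or discontinue". For those lost to follow-up it asks for an effort "to complete the final evaluation". It also says "The Case Report form (CRF) must document the primary reason for withdrawal or discontinuation". Section 8 asks participants withdrawn for an adverse event to attend a clinic visit but names no endoscopy. Section 5.3 describes the biopsies as standard of care.
- **Endpoint and analysis.** The primary endpoint in 1.1 is "Histologic change differences of maximum eos/hpf baseline vs 12 week endoscopy". Sections 1.1 and 9.3 promise intention to treat, and 9.3 defines the set as all enrolled patients with an ID. Section 9.4 gives descriptive summaries and independent-sample t-tests, and leaves further analysis plans open.
- **Missing data.** Sections 10.1.4.1 and 10.1.6 deal with completeness and correction of records. Neither says how a missing outcome is analysed.

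**The concern.** A t-test on change from baseline to week 12 can use only participants who have both counts. The rules in 7.1 remove from the study the participants for whom the diet did not work out in practice, and their week-12 count then depends on an attempt. The intention-to-treat set is defined, but the plan does not say how to analyse the members who lack an outcome.

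The comparison among those with a week-12 count is biased in two situations:

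- Withdrawal is unequal between arms and linked to response.
- Withdrawal is equal in number but linked to response differently in the two arms.

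The routes out (diet failure, intolerance, lost contact) need not have the same link to response, so the bias could favour either diet. A rule chosen after the data are seen would leave the primary result open to question.

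**Working it through.** **Inputs from the documents.** 36 per arm, 50% vs 70% (a difference of 20), SD 30% (9.1); 20% dropout (1.1); independent-sample t-test (9.4). **Assumed.** Significance level and sidedness (not stated), the split of dropout by arm, its link to response, and a normal outcome. Units below are those of the SD of 30 in 9.1, not eos/hpf.

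**1. The plan's own figure.** The standard error is 30·√(2/36) = 7.07, and 20/7.07 = 2.83. One-sided 5%: Φ(2.83 − 1.645) = 88.2%, which matches the stated 88%. Two-sided 5%: Φ(2.83 − 1.96) = 80.7%. So 88% needs a one-sided 5% test with all 36 per arm analysed.

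**2. The plan's own dropout.** 36 × 0.8 = 28.8, about 29 per arm. The standard error becomes 30·√(2/29) = 7.88, and 20/7.88 = 2.54. Power is 81.4% one-sided or 71.9% two-sided.

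**3. Bias with no true difference.** Suppose the lowest share d on a score correlated ρ with response is withdrawn in each arm. Those remaining have their mean shifted by 30·ρ·φ(z_d)/(1 − d), and the bias is the difference of the two shifts. For d = 0.10, φ(z)/(1 − d) = 0.195; for d = 0.30 it is 0.497. At ρ = 1 the bias is 30 × (0.497 − 0.195) = 9.1; at ρ = 0.5 it is half of that, 4.5. Type I errors are from 60,000 simulated trials with a pooled two-sided 5% t-test.

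| Withdrawal by arm | ρ by arm | Bias (units) | Type I error |
|---|---|---|---|
| 10% / 30% | 0 / 0 | 0 | 5% |
| 10% / 30% | 0.5 / 0.5 | 4.5 | 9% |
| 10% / 30% | 1 / 1 | 9.1 | 29% |
| 15% / 25% | 0.5 / 0.5 | 2.2 | 6% |
| 15% / 25% | 1 / 1 | 4.5 | 11% |
| 20% / 20% | 0.5 / 0.5 | 0 | 5% |
| 20% / 20% | 0 / 0.5 | 5.2 | 10% |
| 20% / 20% | 0 / 1 | 10.5 | 30% |

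Reversing the arms reverses the sign.

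**4. Sidedness.** With a one-sided 5% test for FREE and 10%/30% withdrawal, the error is about 14% (ρ = 0.5) or 41% to 42% (ρ = 1) if FREE loses more. At ρ = 0.5 it is about 1% if DED loses more.

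**5. Remission scale.** If a share f of withdrawals are non-remitters and true remission is p, remission among those remaining is (p − d(1 − f))/(1 − d). With p = 0.5 in both arms, f = 1 and 10%/30%: 0.5/0.9 = 55.6% vs 0.5/0.7 = 71.4%, a false 15.9 points. With f = 0.75 it is 52.8% vs 60.7% (7.9 points). With f = 0.5 it is 0.

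**6. Limits of the remedies at 10%/30%.**
- Multiple imputation from baseline and arm removes the bias when withdrawal depends on baseline: 4.7 units falls to 0.2 at an assumed baseline–outcome correlation of 0.5.
- When withdrawal depends on the unseen response (ρ = 0.5), 2.4 to 4.2 of about 4.5 units remain, for baseline correlations of 0.7 down to 0.3.
- If withdrawals in truth respond like completers, return to baseline with an assumed mean improvement of 50 units gives (0.30 − 0.10) × 50 = 10 units against the arm that loses more (two-sided error 25%).
- Under the same truth, missing = non-remission gives 0.5 × 0.9 = 45% vs 0.5 × 0.7 = 35%, a false 10 points (two-sided error 13.7%).

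**The case against.** The strongest reply is that the plan recovers some outcomes. Section 7.1 asks for information on everyone who withdraws and for an effort at the final evaluation for those lost to follow-up, and the biopsies are standard of care. The efficacy set in 9.3 includes all enrolled patients, so the natural reading is that a recovered count is analysed in the assigned arm. This stands. A reader might infer that everyone withdrawn drops out of the analysis, but the documents support only that those without a week-12 count do. Stating that recovered counts are used is a clarification.

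Three other stronger readings also go beyond the documents:

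- **That the bias favours FREE.** FREE adds a restriction to DED, so heavier loss there is plausible. The documents give one combined dropout figure and no link to response, so neither size nor direction can be stated.
- **That the illustration sets a sensitivity range.** In the same model the gap between completers and withdrawals is ρ·30·φ(z_d)/(d(1 − d)), which reaches 58.5 units at ρ = 1 and d = 0.10. The documents give no SD in eos/hpf, so this figure cannot be carried to the endpoint.
- **That 6.3 and 7.1 flatly contradict each other.** Section 6.3 may only say who judges noncompliance, and 7.1 what follows. This is a minor point of wording.

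What remains after these concessions is that no rule exists for a count that is truly missing.

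**Conclusion.** The concern holds in this form. Mandatory withdrawal in 7.1, follow-up that is only attempted, and a t-test with no missing-count rule together mean that the promised intention-to-treat comparison is in practice one of participants with a week-12 count. This is more than missing detail, because the withdrawal rule itself works against the stated analysis principle for the primary endpoint.

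What rests on document figures is the expected loss to about 29 of 36 per arm. The bias and error rates are illustrations that depend on the assumed splits, links, normal outcome and test level. They run from no bias to roughly half of the planned 20-unit effect, and in either direction. Equal withdrawal is harmless only if its link to response has the same effect in both arms.

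The must-fix label attaches to the pre-specified analysis rule. Confidence in the textual finding is high.

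**What to change.** 1. **Follow-up.** Leave clinical decisions to stop a diet or to perform an endoscopy as they are. State that stopping the diet does not by itself end study follow-up. State that the already planned week-12 assessments are sought where consent continues and the investigator does not object, and that any week-12 standard-of-care biopsy is analysed in the assigned arm.
2. **Analysis rule.** Before the data extraction described in 10.1.4.1, pre-specify one primary rule for missing week-12 counts that fits the change-in-count endpoint, such as multiple imputation using baseline count and arm. Add a delta-adjusted or tipping-point analysis that varies the assumed outcome of withdrawals separately by arm and in both directions. Include return to baseline as one case, and set the delta range in eos/hpf from the trial's own scale. Use missing = non-remission only in a supportive responder analysis (the success threshold in section 3).
3. **Minor.** The sponsor should reconcile 6.3 and 7.1 on who decides withdrawal for noncompliance. Tabulate by arm the withdrawal reasons that the CRF already records.

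Version 13 is dated 22 July 2020 and the planned end in 1.1 is 31 July 2020, nine days later. If follow-up can no longer be changed, item 2 is the part that must be done.

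**Cost.** Mainly protocol and SAP wording, with modest coordinator effort to keep contact. No missing-data rule is neutral, the estimate may be less favourable than among completers, and the conclusion may depend on the assumed delta if many counts stay missing.

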7.2 PARTICIPANT DISCONTINUATION/WITHDRAWAL FROM THE STUDY

The participant and/or the parent(s)/legal representative(s) are free to withdraw the participant from the study at any time, without prejudice to continued care.

7.3 LOST TO FOLLOW-UP

Participants will be withdrawn from the study / considered LTFUP if the coordinator is unable to make contact by telephone to complete weekly assessments for at least 3 sequential weeks.

8 STUDY ASSESSMENTS AND PROCEDURES

At all visits and telephone contacts, participants will be instructed to call the investigator if any intolerable and/or serious AEs (SAEs) occur before the next visit or contact. After participants begin study medication, if any AEs necessitate a participant's withdrawal from the study, the participant should come in for a clinic visit as soon as possible after the occurrence of the AE. Planned clinic visits should be scheduled as indicated in Section 1.3

Screening/Baseline: Visit 1 (Day 1)

At Visit 1, participants will be evaluated for their suitability for enrollment. It is acceptable for this visit to be conducted on more than 1 day; however, all results of Visit 1 assessments should be available prior to randomization. Prior to the conduct of any study-related procedures, a complete explanation (both verbal and written) of the nature and purpose of the study will be given to the participant's parent(s)/legal representative(s) by the investigator (or designee). The parent(s)/legal representative(s) of the participant is required to sign and date the IRB approved informed consent if he/she decides to participate in the study.

The participant's eligibility for the study will be determined on the basis of the inclusion/exclusion criteria, signature of an informed consent prior to any study-related procedures or evaluations, and the results of the following assessments.

Screening Procedures

1. Informed consent
2. Review Inclusion/exclusion criteria
3. Medical History
4. Demographics
5. Concomitant Medications

Baseline Procedures

1. Randomization
2. EREF** score
3. PedsQL-EoE

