1.2 SCHEMA

1.3 SCHEDULE OF ACTIVITIES

Procedures	Screening Day -7 to 1	Enrollment/Baseline Visit 1, Day 1	Study Visit 2 (FUP Call) Day 7 (week 1) +/-2 days	Study Visit 3 (FUP Call) Day 14 (week 2) +/- 2 days	Study Visit 4 (FUP Call) Day 21 (week 3) +/-2 days	Study Visit 5 (FUP Call) Day 28(week 4) +/-2 days	Study Visit 6(FUP Call) Day 35 (week 5) +/-2 days	Study Visit 7 (FUP Call) Day 42 (week 6) +/-2 days	Study Visit 8 (FUP Call) Day 49 (week 7) +/-2 days	Study Visit 9 Day 56 (week 8) +/-14 days	Study Visit 10 Day 63 (week 9) +/-14	Study Visit 11 Day 70 (week 10) +/-14	Study Visit 12 Day 77 (week 11) +/-14	Study Visit 13 Day 84 (week 12) +/-14
Informed consent	X													
Review Inclusion/Exclusion Criteria	X													
Medical History	X													
Demographics		X												
Pathologist Questionnaire / Peak Eosinophils per high power field (Eos/hpf)	X													X
Randomization		X												
Personal Information		X												
Height and Weight		X												X
Eosinophilic Esophagitis Endoscopic Reference Score (EREF)		X												X
Diet Education		X												
Dietician Follow Up Calls			X			X			X				X	
Three-day Diet Diary		X												X
Quality of Life (PedsQL EoE)(Parent & Child)		X				X*				X*				X*
Pediatric Eosinophilic Esophagitis Symptom Severity Module (PEESS)(Parent & Child)		X				X*				X*				X*
Adverse Event Reporting (Safety Q)		X				X*				X*				X*

Procedures	Screening Day -7 to 1	Enrollment/Baseline Visit 1, Day 1	Study Visit 2 (FUP Call) Day 7 (week 1) +/-2 days	Study Visit 3 (FUP Call) Day 14 (week 2) +/- 2 days	Study Visit 4 (FUP Call) Day 21 (week 3) +/-2 days	Study Visit 5 (FUP Call) Day 28(week 4) +/-2 days	Study Visit 6(FUP Call) Day 35 (week 5) +/-2 days	Study Visit 7 (FUP Call) Day 42 (week 6) +/-2 days	Study Visit 8 (FUP Call) Day 49 (week 7) +/-2 days	Study Visit 9 Day 56 (week 8) +/-14 days	Study Visit 10 Day 63 (week 9) +/-14	Study Visit 11 Day 70 (week 10) +/-14	Study Visit 12 Day 77 (week 11) +/-14	Study Visit 13 Day 84 (week 12) +/-14
Concomitant medication review	X	X		X	X		X	X		X			X	X
Coordinator Call				X	X		X	X		X	X		X	
Payment to Part. for Completed Visit		X				X				X				X

* REDCap survey – completed by participant/parent

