4. PEES
5. Diet Counseling
6. Three-day diet diary
7. Concomitant Medications (review if baseline and screening visits do not take place on the same day)
8. Payment to Participant for Completed Visit

* Histological outcomes (e.g. maximum eos/hpf) will be assessed by an experienced study pathologist.

** All GI providers will be trained to assess EREFs prior to the initiation of the trial. They will complete the evaluation for all suspected cases of EoE.

Randomization

Participants will be randomized to either the DED or FREE diet.

Intervention

Participants will receive diet education. A trained nutritionist/dietician will provide counseling regarding the foods allowed and foods not allowed on each diet. Participants will be given written instructions and daily diet diaries for their own use.

Coordinator Telephone Contacts: (Weeks 2, 3, 5, 6, 8, 9, and 11; days 7 through 77)

Beginning with Telephone Contact at Day 7, the coordinator will assess AEs, review concomitant medications, review withdrawal criteria, and assess difficulty adhering to the diet. Participants will be sent invitations from REDCap to complete required questionnaires. The coordinator will remind participants to complete the questionnaires. The participant will be instructed to call the investigator if any intolerable and/or SAEs occur. If any change in the study medication is required, the participant should come in for a clinic visit as soon as possible.

Coordinator Call:

1. Diet/Medication Review & Adherence Assessment
2. Review concomitant medications
3. Review withdrawal criteria
4. Review previously reported AEs
5. Survey reminder

Dietician Telephone Contacts: (Weeks 1, 4, 7 and 11; days 7 through 77)

Beginning with Telephone Contact at Day 7, the Dietician will assess adherence to the diet, answer questions regarding the diet, assess changes in weight, and assess difficulty adhering to the diet.

Participant Questionnaires (Baseline, Week 4, Week 8, and Week 12; days 1 through 84)

Participant Questionnaires (via REDCAP)

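### Section 8 wants Visit 1 results in hand before randomization, but its own baseline list and the Day 1 schedule let PedsQL-EoE, PEESS and the three-day diary fall after allocation

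*Combined protocol and SAP*

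**What the plan says.** Four places bear on when the baseline is taken.

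- **Section 8, Screening/Baseline: Visit 1.** The rule is that "all results of Visit 1 assessments should be available prior to randomization". The same sentence allows the visit to be spread over more than one day.
- **Section 8, Baseline Procedures.** The numbered list opens with "1. Randomization". EREF is item 2, PedsQL-EoE item 3 and PEESS item 4. Then come "5. Diet Counseling" and "6. Three-day diet diary".
- **Section 1.3, Schedule of Activities.** Randomization, EREF, diet education, the diary, PedsQL-EoE and PEESS are all marked in the Day 1 column. None of them is marked at baseline in the column headed "Screening Day -7 to 1", although consent and the eligibility review are.
- **Section 6.1.1.** The 12 weeks of participation are counted from the date of enrollment and randomization.

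The Synopsis defines both tertiary endpoints, symptoms (PEESS) and quality of life (PedsQL-EoE), as baseline against 12 weeks. Section 5.3 describes blinding for the central pathologist only. Section 9.4 plans independent-sample t-tests and states no adjustment for baseline.

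**The concern.** PedsQL-EoE and PEESS are filled in by parents and children. No masking of families is described, and they are counselled on a specific diet, so they will know their arm. If the questionnaires are completed after allocation, disappointment with one diet or apprehension about the other can colour the answers. The score called baseline then carries an effect of the assignment, and the change from it no longer has a clean starting point. This cannot be repaired afterwards.

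The diary raises a simpler difficulty. It covers three days but is marked only on the day of randomization and diet education. If it starts then, it describes the first days on the assigned diet. The trial would have no record of dairy and additive intake before the diet with which to compare the week-12 diary.

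**Working it through.** The plan states no figure on this point. The check is therefore mainly a comparison of texts, followed by an illustration of size.

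**1. Order and timing, item by item**

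| Item | Place in Section 8 list | Section 1.3 column | Can it precede allocation? |
|---|---|---|---|
| Randomization | 1 | Day 1 | – |
| EREF | 2 | Day 1 | Very probably yes: scored at the diagnostic endoscopy |
| PedsQL-EoE | 3 | Day 1 | Yes, if the Section 8 rule overrides the list |
| PEESS | 4 | Day 1 | As for PedsQL-EoE |
| Diet counselling | 5 | Day 1 | Not applicable |
| Three-day diary | 6 | Day 1 | Only if started before Day 1, or if Visit 1 is split before allocation; nothing asks for either |

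The two sources differ on one detail. The Section 8 list puts the questionnaires after randomization but before counselling. The schedule prints the diet education row above the questionnaires, within the same column.

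**2. EREF.** The Section 8 footnote says of the GI providers: "They will complete the evaluation for all suspected cases of EoE". A suspected case is scored at the diagnostic endoscopy. Section 5.1 requires the diagnostic biopsy to be no more than 12 weeks before enrollment, and no Day 1 endoscopy is listed.

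**3. Primary endpoint.** Peak eos/hpf is marked at screening in Section 1.3 and is read by a pathologist blinded to diet (Section 5.3). The order of Day 1 procedures does not touch it.

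**4. How a baseline shift would act.** Let knowledge of the arm move the baseline mean in one arm by b, with no true effect and no effect on week 12. Change is week 12 minus baseline, so the expected between-arm difference in change is −b: same size, reversed sign.

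**5. Illustrative size.** Inputs: n = 36 per arm (Section 9.1). Assumed, because the documents give no values: b in SD units, equal SDs at both times, correlation r between baseline and week 12, and a two-sided 5% test of change scores.

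- SD of change = √(2(1 − r)). At r = 0.5 this is 1 SD.
- SE of the difference = SD of change × √(2/36) = 1 × 0.236 = 0.236 SD.
- d = b/SE. False-positive rate = Φ(d − 1.96) + Φ(−d − 1.96).
- b = 0.1: d = 0.424; 0.0623 + 0.0086 = 0.071.
- b = 0.2: d = 0.849; 0.1332 + 0.0025 = 0.136.

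The same formula over a wider range:

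| r | b = 0.1 | b = 0.2 | b = 0.3 |
|---|---|---|---|
| 0.3 | 6.5% | 11.1% | 19.0% |
| 0.5 | 7.1% | 13.6% | 24.7% |
| 0.7 | 8.5% | 19.5% | 37.6% |

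With the Synopsis's 20% dropout, n = 0.8 × 36 = 28.8 per arm. At r = 0.5, SE = √(2/28.8) = 0.264. For b = 0.1, d = 0.379 and the rate is 0.0570 + 0.0097 = 6.7%. For b = 0.2, d = 0.759 and the rate is 0.1149 + 0.0033 = 11.8%. The picture is the same, slightly weaker.

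**The case against.** The strongest reply is that the Section 8 rule is itself the safeguard and the numbered list is only an inventory. Much of this stands.

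- No text makes the list a sequence, and another list in Section 8 cannot be one: the Final Assessment puts the pathology questionnaire ahead of EREF, although the biopsy comes from the endoscopy. After the baseline list, separate headings for randomization and then intervention fit the rule.
- The lead site randomizes only after being notified of enrollment (Section 6.2), so a site can satisfy the rule and still complete every item.
- The diary is not an endpoint and is not in the analysis plan. Its purpose is never stated, so its use as a record of usual diet is an inference, though a natural one.
- Section 9.4 does not say that change scores will be tested. If week-12 values alone are compared, the mechanism in the calculation disappears.

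A reader might infer that the plan prescribes baselines after allocation, or that the rule and the list cannot both be obeyed. The documents do not support that: it holds only if the numbering is mandatory, which is nowhere stated. A reader might also infer that families are counselled before answering the questionnaires. The Section 8 list has it the other way round; only the diary follows counselling there.

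What the reply does not answer is that one sentence, worded as a recommendation, stands against a list headed by randomization and a schedule with no earlier slot. For the diary, the difficulty arises from the Day 1 marking alone, without treating the list as a sequence.

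**Conclusion.** The conflict is real and worth correcting, but it is limited. The rule in Section 8 does not match the list below it or the schedule in Section 1.3. As written, the plan allows PedsQL-EoE and PEESS baselines to be taken after the arm is known, and it gives the three-day diary no place before the diet starts.

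The reach is the two tertiary endpoints and the diary. It would be tempting to extend the point to EREF because EREF also follows randomization in the list, but the footnote and the biopsy window place its scoring before enrollment. The primary endpoint is untouched.

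The size is unknown. The 7% to 14% range is not an estimate for this trial; it follows from an assumed 0.1 to 0.2 SD shift, r = 0.5, 36 per arm and a change-score test. That families know their diet is inferred from the absence of any described masking and from the counselling; the protocol does not use the term open-label.

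**What to change.** Reconcile Sections 1.3 and 8 so that list, schedule and rule say the same thing:

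1. Mark PedsQL-EoE, PEESS and the baseline three-day diary in the existing Day -7 to 1 window, after consent.
2. Require all three to be completed and entered before the lead site releases the allocation. A check at that step is enough, since the lead site already performs randomization and Section 8 already places the baseline questionnaires in REDCap.
3. Put randomization after these items, and diet education last.
4. State that baseline EREF is the score from the diagnostic endoscopy.
5. At week 12, have PedsQL-EoE and PEESS completed before the family hears the endoscopy or biopsy result. The Final Assessment lists both instruments after the pathology and EREF items, and nothing fixes their timing relative to disclosure.

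The cost is a wording amendment and a check on existing forms; no assessment is added. The downside is practical. Section 8 contemplates screening and baseline on the same day. Families who would have done both together will need the diary a few days earlier, so randomization and diet education may move to a later contact.
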